6.1.3 Procedure for reporting serious adverse events

In the event of the occurrence of any clinical AE or abnormal laboratory test value that is serious or medically important during the course of the study or the post-treatment period, irrespective of the treatment received by the subject, the investigator is obliged to immediately inform the Investigator-Sponsor.

The immediate report by the investigator to the Investigator-Sponsor shall be followed by detailed, written reports using the SAE report form (for an “initial” SAE or for “follow-up” information on a previous SAE). The immediate and follow up reports shall identify subjects by unique code numbers assigned to the latter.

For names, addresses, telephone and fax numbers, see SAE report form.

The Investigator-Sponsor shall ensure that all reporting requirements according to the respective national law are followed. “Expectedness” to be assessed with regard to the valid IB for cetuximab. “Expectedness” with respect to a comparator or a concomitant anti-cancer treatment, if applicable, is to be assessed according to either the respective IB or versus the Product Information. A CIOMS-1 format shall be used for submitting expedited reports to the competent authorities, the ethics committee and to all investigators involved in this study according to all appropriate national and international laws. Where necessary, the CIOMS-1 form shall be accompanied by the relevant pages of the case report form.

Cetuximab **SUSARs** represent Serious Adverse Events related to cetuximab (=Adverse Reactions), considered “unexpected” with regard to the valid IB for cetuximab.

With respect to cetuximab, the Investigator-Sponsor shall only copy Merck in any cetuximab individual case safety report, which has been submitted expeditedly to the competent authorities. The report to Merck shall be sent via Fax only at the same time of reporting to the competent authorities.

The Investigator-Sponsor shall ensure that for a reported death of a subject, the investigator shall supply the Investigator-Sponsor and the Ethics Committee with any additional information as requested.

6.1.4 Monitoring of subjects with adverse events

Any AE that occurs in the course of a clinical study must be monitored and followed up until the End of Study Visit. Ongoing adverse events related to study treatment will be followed for 6 weeks (skin toxicities until outcome is known) after end of treatment. In addition SAEs must be reported via a SAE report form (see section 6.1.1.3 Procedure for reporting serious adverse events).

It is the responsibility of the investigator that any necessary additional therapeutic measures and follow-up procedures are performed.

6.1.5 Overdose and intoxication with the study drug

There is no experience with single doses of cetuximab higher than 500 mg/m² body surface area in human clinical trials. In the event of a drug overdose occurring in the course of the present study, this must be reported as a SAE.

6.2 Laboratory assessments

All clinical laboratory evaluations will be performed at the local laboratory of the investigational site complying with GCP and local requirements.

A safety laboratory examination consisting of hematology must be performed at baseline, weekly during radio-immunochemotherapy and at the end of treatment evaluation. Clinical chemistry must be performed at baseline, on day 1 of every course (every 4 weeks) of the radio-immunochemotherapy, and at the end of treatment evaluation.

Women of childbearing potential must have a negative serum or urine pregnancy test (minimum sensitivity according to local regulation) within 7 days prior to the start of the study medication.

Safety laboratory parameters

- Hematology (5 ml)
Leucocytes, neutrophils, platelets, erythrocytes, hemoglobin
- Clinical chemistry (10 ml)
Sodium, potassium, calcium, magnesium, creatinine, bilirubin, SGOT, SGPT, LDH, alkaline phosphatase, γ -GT
- Pregnancy test (if applicable)
Male or female patients must be practicing a medically accepted contraception.

6.3 Vital signs and physical examination

A physical examination including weight and height will be performed at screening.

Resting blood pressure (systolic/diastolic, supine, after 5 minutes rest) and heart rate (after 5 minutes rest) will be measured at screening, weekly during radio-immunochemotherapy and at the end of treatment.

7 Schedule of assessments

The table below summarizes the assessments to be made during (pre)-screening and during the study. Descriptions of the methodology to be used are given in the following sections.

Table 8: Overview of assessments during screening and during the study.

Screening and During Study	Includes
Informed Consent	
 • Written informed consent for participation in the study

Medical History	
 • Demographic data • Tumor diagnosis • Check of inclusion and exclusion criteria • Previous relevant diseases other than esophageal cancer • Concomitant medications within 4 weeks preceding study start
Vital signs	
 • Resting heart rate • Resting blood pressure (systolic/diastolic) • Height / weight • Body surface area
Performance status	
 • Karnofsky performance status
Safety lab	
 • Hematology • Clinical chemistry • Pregnancy test (where applicable)
Cardiac evaluation	
 • ECG and measurement of ejection fraction (LVEF)
Lung function test	
 • FEV₁
Clinical staging and imaging	
 • Endoscopy • Endoscopic ultrasound (optional) • CT • DC-MRT (in selected centers)

7.1 Screening examinations

After the patient has signed the informed consent, all eligibility criteria will be checked. Patients may only be enrolled, if all inclusion criteria and none of the exclusion criteria are met.

If frozen tissues or immunohistochemical blocks from previous biopsies are available at the local study site or the regional Pathology Department, they should be transported to Mainz for further analysis.

7.1.1 Examinations within 4 weeks prior to treatment start

- Written informed consent for participation in the study
- Medical History
- Clinical staging (endoscopy incl. biopsy)
- Endoscopic ultrasound

- Tumor Assessment CT/MRI chest and abdomen
- ECG and LVEF
- FEV₁
- Evaluation by a surgeon with respect to resectability
- Tissue immunohistochemistry

7.1.2 Examinations within 7 days prior to treatment start

- Height, weight, vital signs
- Karnofsky-Performance Status
- Hematology (leucocytes, neutrophils, platelets, erythrocytes, hemoglobin)
- Clinical chemistry (sodium, potassium, calcium, magnesium, creatinine, bilirubin, , SGOT, SGPT, LDH, alkaline phosphatase, γ -GT)
- Pregnancy test in women of child-bearing potential
- Serum sample (10 ml) and whole blood sample (10 ml) for EGFR and ligands determination (if patient agrees to participate in translational study)

7.2 Evaluations during radio-immunochemotherapy

7.2.1 Weekly examinations

- Vital signs
- Weight
- Hematology (leucocytes, neutrophils, platelets, erythrocytes, hemoglobin)
- Clinical signs and symptoms, toxicity according to the NCI-CTC version 4.0
- DC-MRT: at day 7 (+/-2) or day 14 (+/-2) of the first cycle (in selected centers)

7.2.2 Examinations every 4 weeks

- Karnofsky-Performance Status
- Biochemistry (sodium, potassium, calcium, magnesium, creatinine, bilirubin, SGOT, SGPT, LDH, alkaline phosphatase, γ -GT)

7.2.3 Examinations after 4 weeks of treatment

- Endoscopy (incl. biopsy, if patient agrees to participate in translational study)
- Endoscopic ultrasound (optional)
- Tumor assessment (CT/MRI chest and abdomen)
- serum sample (10 ml) for EGFR and ligands determination (if patient agrees to participate in translational study)
- Tissue immunochemistry (if patient agrees to participate in translational study; immunohistochemical blocks should be transported to Mainz for further analysis)
- Re-evaluation by a surgeon with respect to resectability*

**If resectability has been achieved, radiochemotherapy +/- cetuximab is stopped after 45 Gy, and the patient is referred to surgery. If resectability has not been achieved, radiochemotherapy +/- cetuximab is continued as indicated above.*

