
Planned treatment duration per subject
	
The planned treatment duration per patient is 14 weeks.
 
The planned duration of radio-immunochemotherapy is 6.5 to 7 weeks.
 
Patients will be withdrawn at any time during the study if they develop unacceptable toxicities or if they withdraw the consent to participate in the trial.
 
Ongoing adverse events related to study treatment will be followed for 6 weeks (skin toxicities until outcome is known) after end of treatment.

Primary target variable
	
2-year overall survival (OS)

Secondary efficacy target variables
	
 • 1-year OS • 1-year and 2-year PFS • 1-year and 2-year LC • 1-year and 2-year MFS • Overall response rate (RECIST Version 1.1)

Tolerability/safety variable(s)	Toxicity (NCI-CTC 4.0)
Pharmacokinetics	Not applicable
Pharmacodynamics, -genomics and/or -genetics	Not applicable
Quality of life and pharmacoeconomics	Quality of Life (EORTC QLQ-C30 and QLQ OES18)
Other assessments	Not applicable
Data Safety Monitoring Board	
A Data Safety Monitoring Board (DSMB) will be implemented to formally review safety data when 20 patients and again when 67 patients (50% of the entire cohort) are randomized and have completed 4 weeks of treatment. The DSMB will focus on safety and survival data only. In addition, the DSMB will be provided with regular reports every 6 months summarizing the same safety information used for the formal review.
 
The key safety parameters to be monitored will be
 
 • Overall incidence of patients with any CTCAE-grade III/IV adverse event • Incidence of Serious Adverse Events (SAEs) 
In case of significant excess toxicity associated with the experimental arm, the DSMB may decide together with the Sponsor to stop the trial early due to safety concerns.

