5.5.1 Technique and dosage of radiotherapy

Radiotherapy starts on the first day of the chemotherapy following cetuximab infusion and prior to the 5-FU and cisplatin infusions. A total of 59.4 Gy (at the reference point according to ICRU 62) will be delivered in daily fractions of 1.8 Gy for 6.5 - 7 consecutive weeks (5 fractions/week). Irradiation will be performed using high energetic photons, preferably a linear accelerator with photon energies of at least 6 MV. The 95% isodose should cover the target volume.

Isocentric 3- or 4- field techniques with individual absorbers will be used. To adequately perform planning a treatment simulator and computerized 3-D-treatment planning must be used. The CT-slices should be contiguous and not thicker than 10 mm, preferably 5 mm with clip labelling. Optimal patient positioning to reduce normal tissue damage - if necessary including the use of a belly board should be performed.

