5.5.1 Adverse reactions and dose modifications of radiotherapy

Expected acute adverse reactions of the radiotherapy are esophagitis and dysphagia. These reactions may be aggravated by the concurrent chemotherapy. Treatment will be symptomatic. Generally, these acute adverse reactions abate within two to four weeks following completion of radiotherapy. In severe cases, the treatment may be interrupted for up to one week, if deemed necessary by the responsible radio-oncologist. If radiotherapy has to be stopped due to adverse reactions, the LKP has to be informed. Rare severe events are e.g.: skin reactions, pneumonitis, arrhythmia.

Interruption or termination of radiotherapy due to adverse reactions should be based on the following recommendations:

Table 7: Interruption of radiotherapy in case of gastrointestinal toxicity

Toxicity grade	esophagitis/dysphagia	Radiotherapy
0	none	continue
1	Mild dysphagia, but can eat regular diet	continue
2	Dysphagia requiring predominantly liquid, pureed or soft diet	Continue
3	Dysphagia, requiring feeding tube, IV hydration or hyperalimentation	Interruption of radiotherapy for a maximum of 7 days. If the esophagitis/dysphagia does not resolve, the radiotherapy should be stopped.
4	Complete obstruction (cannot swallow saliva); ulceration with bleeding not induced by minor trauma or abrasion or perforation	Stop radiotherapy

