8.1 Analysis set descriptions

Safety Analysis Set

The safety population includes all patients who received at least one dose of trial medication and for whom at least one post-baseline safety measurement is available.

Full Analysis Set

The Full Analysis Set includes all patients who received at least one dose of trial medication and for whom at least one post-baseline efficacy measurement is available.

Per Protocol Set

This population includes all patients with at least six weeks of trial medication plus all patients who discontinued the study prematurely due to lack of efficacy, death or toxicity. Detailed criteria will be defined before analysis.

All safety analyses will be performed on the Safety Analysis Set. For efficacy analysis of the trial, the primary analyses will be based on the per-protocol set. Additional analyses will be performed on the Full Analysis Set for sensitivity purposes.

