8.4 Sample size calculation

This phase II study is an explorative randomized study with 2 parallel groups. Using a standard single-stage phase II design by FLEMING (1981), $n = 62$ patients evaluable for efficacy have to be recruited. As a similar number of patients is to be recruited to the standard arm, a total number of 124 patients is required. The standard treatment control group serves to reduce some of the result variability which is typically encountered in single-arm phase II trials, especially caused by patient selection phenomena and investigator bias. To cover potentially drop outs 67 patients per arm will be recruited.

The OS rate after 2 years is chosen as primary efficacy endpoint. The estimation of the efficacy rate of 40% of the reference group is based on the findings of several studies [49-54]. Therefore, the respective experimental therapy arm would be rated as insufficiently active, if the observed OS rate at 2 years is 40 % or lower.

On the other hand, the experimental therapy would be considered to be a very promising candidate for further development (e.g. in a phase III trial), if the true OS rate at 2 years amounted to 45 % or more.

Probability to accept the experimental therapy as promising ($> 45\%$ OS rate) with respect to efficacy, in spite of a true OS rate of $\leq 40\%$: 5% (type I error).

Probability to reject the experimental therapy as not sufficiently efficient ($\leq 40\%$), although the true OS rate is promising ($> 45\%$): 20% (type II error, corresponding to a power of 80%).

However, the last patient will be randomized on December 31, 2016 at the latest, which is 2.5 years later than originally planned. Based on number of patients randomized until end of July and who received study treatment ($n=66$) it is expected that the total number of patients in the Full Analysis Set (FAS) will be between 72 and 78 patients, while the number of patients in the Per Protocol Population is expected to be between 66 and 72 patients.

The final conclusion of the phase II trial will depend on the definite OS rate (and its confidence interval), the respective findings in the 5-FU/cisplatin reference arm, as well as the information on type, frequency and severity of toxicities.

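### The six-week rule of the primary Per Protocol Set makes no provision for patients sent to surgery after 45 Gy and can exclude these protocol-adherent responders

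*Combined protocol and SAP*

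**What the plan says.** The resectability branch is planned for both arms. A surgeon re-evaluates each patient after 4-4.5 weeks of treatment, at 36-41.4 Gy. If the tumor has become resectable, section 7.2.3 and the matching synopsis entry state that "radiochemotherapy +/- cetuximab is stopped after 45 Gy, and the patient is referred to surgery". The treatment descriptions in the synopsis, 4.1 and 5.5 name only radiotherapy as stopping at 45 Gy. Section 7.5.2 provides a residual-tumor classification for patients who have surgery, so such patients are expected.

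For efficacy, section 8.1 states that "the primary analyses will be based on the per-protocol set"; the Full Analysis Set is for sensitivity. The Per Protocol Set takes patients with "at least six weeks of trial medication plus all patients who discontinued the study prematurely due to lack of efficacy, death or toxicity". It adds: "Detailed criteria will be defined before analysis". The term *trial medication* is not defined. Sections 4.2.4 and 4.2.6 do not mention the planned stop for surgery as an end of treatment.

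**The concern.** The rule admits early stops of an unfavorable kind and is silent on the one early stop that the protocol itself orders because treatment worked. A patient treated exactly as planned can therefore fail the primary set. Whether that happens depends on tumor response, which is observed after randomization and may be affected by treatment.

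Two results are exposed: the 2-year survival rate in the cetuximab arm, which is judged against 40%, and the log-rank comparison of the arms in 8.4. The trial is open-label, so a membership rule settled late would be settled by people who can know the allocations.

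**Working it through.** **Inputs.** Fractions of 1.8 Gy, five per week (5.5). Radiotherapy starts on the first chemotherapy day (5.5.1): day 8 in Arm A, day 1 in Arm B (4.1). Chemotherapy before the 45 Gy stop: days 8-11 and 36-39 in Arm A, days 1-4 and 29-32 in Arm B. Cetuximab is weekly from day 1 in Arm A. Six weeks = 42 days. Treatment on weekdays without delays is assumed.

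**Reproducing the plan's timing.** 59.4 / 1.8 = 33 fractions; 33 / 5 = 6.6 weeks, as stated (6.5-7). 36 / 1.8 = 20 fractions = 4.0 weeks, and 41.4 / 1.8 = 23 fractions = 4.6 weeks, close to the stated 4-4.5.

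**The 45 Gy stop.** 45 / 1.8 = 25 fractions; 25 / 5 = 5.0 weeks.
- Arm B: the last fraction is on day 33 with a Monday start and day 35 with a Tuesday-Friday start (33 / 7 = 4.7 weeks; 35 / 7 = 5.0 weeks).
- Arm A: seven days later, day 40 or day 42 (5.7 or 6.0 weeks). Cetuximab falls on days 1, 8, 15, 22, 29 and 36, which is six infusions; the next would be day 43.

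**Against the six-week rule:**

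| How the weeks are counted | Arm A | Arm B |
|---|---|---|
| Day 1 to last radiotherapy day | 40-42: borderline | 33-35: short |
| Day 1 to last drug day | 39: short | 32: short |
| Weekly treatment units | 6 infusions: meets | 5 weeks: short |
| First day of radiochemotherapy to last radiotherapy day | 33-35: short | 33-35: short |
| Whole four-week courses started | 2 x 4 = 8 weeks: meets | 2 x 4 = 8 weeks: meets |

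On none of these counts is Arm A excluded more readily than Arm B. The differences between the arms come from the one-week cetuximab lead-in.

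**Comparison within Arm B.** A non-resected patient given all 33 fractions finishes on day 45 (Monday-Wednesday start) or day 47 (Thursday-Friday start) and passes. By radiotherapy days, the rule thus separates resected from non-resected patients who were both treated as planned. Table 7 allows "Interruption of radiotherapy for a maximum of 7 days"; that would move the Arm B stop to 33 + 7 = 40 or 35 + 7 = 42, so 42 is reached only with the longest interruption and a start other than Monday.

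**Scale (illustration only).** With 14 of 35 patients alive at 2 years (40.0%), removing one survivor gives 13/34 = 38.2%, or 1.8 points lower. More generally, assume true 2-year survival of 40% in both arms, a resected share s with 2-year survival r, and exclusion from Arm B only. The Arm B estimate becomes (0.40 - s x r) / (1 - s). With s = 10% and r = 60%: (0.40 - 0.06) / 0.90 = 37.8%, a spurious 2.2 points. Over s = 5-10% and r = 50-70% the range is 0.5 points (0.40 - 0.375/0.95) to 3.3 points (0.40 - 0.33/0.90).

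**The case against.** The strongest reply is that the rule speaks of medication, and radiotherapy is not clearly medication; section 5.8 on compliance names only cetuximab, cisplatin and 5-FU. By drug days both arms miss 42, and by whole courses both pass. This stands. A reader might infer that the rule systematically removes responders from the control arm and so favors cetuximab. The documents do not support that as a general statement: it needs a count on which Arm A passes and Arm B fails. Where both arms fail, the documents give no direction for the comparison.

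It can also be said that the definition is openly unfinished and that the Full Analysis Set, which has no six-week rule, will be reported. Both are true, but neither repairs the text. The deferred criteria could close the gap and nothing commits them to do so, and the Full Analysis Set is not primary. Section 8.3.3 disclaims a formal, rigorous comparison, and 8.4 rests the conclusion on the survival rate with its interval, the reference arm and toxicity. That softens the log-rank concern but not the concern about the rate itself.

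A further reply is that several sections stop only radiotherapy. However, 7.2.3 and the synopsis visit schedule stop the drugs explicitly.

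Finally, the number affected may be small. Section 8.4 says "the number of patients in the Per Protocol Population is expected to be between 66 and 72 patients", against 72-78 in the Full Analysis Set: 72 - 66 = 78 - 72 = 6 fewer, both arms and all reasons together. A reader might take these six to be the resected patients; the text does not say so. The figure does argue against illustrations with large exclusions: 20% of 36 is already 7.2 patients from one arm.

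**Conclusion.** The gap is real on the text. The primary set can exclude adherent patients who stopped because the tumor became resectable, while it keeps those who stopped because treatment failed. In Arm B they fall short by elapsed days and by treatment weeks; in Arm A it depends on a term that the plan leaves undefined; counted as whole courses, neither arm loses anyone.

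If resected patients live longer (an assumption), exclusion lowers the affected arm's 2-year survival. In Arm A that works against cetuximab when the rate is judged against 40%. A differential bias toward cetuximab follows only on the counts where Arm A passes and Arm B fails. The documents give no resection rate and no survival for resected patients, so the size of any bias cannot be computed, and the percentages above show scale only. The point should be settled before the analysis; confidence is medium, because the gap is certain but its frequency is unknown.

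**What to change.** Add to 8.1:

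*Patients in either arm whose study treatment was stopped after 45 Gy because resectability was achieved are included in the Per Protocol Set.*

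Also define weeks of trial medication in the same way for both arms, counted from the first day of radiochemotherapy, so that the lead-in week gives Arm A no advantage. On that count resected patients in both arms remain under six weeks, so the inclusion sentence is still needed. With it, exclusions for this reason are zero in both arms on every count.

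If the planned stop is to be listed as an end of treatment, it belongs in 4.2.6. Placing it among the withdrawal reasons in 4.2.4 would label adherent patients as withdrawn.

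The cost is one sentence and one definition in 8.1, and optionally a line in 4.2.6, fixed before the analysis. No extra patients or procedures are needed.

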7.3 End of Treatment Evaluations

After completion of the radio-immunochemotherapy or at the time of premature withdrawal for any reason the following assessments will be performed:

- Vital signs
- Karnofsky performance status
- Hematology (leucocytes, neutrophils, platelets, erythrocytes, hemoglobin)
- Clinical chemistry (sodium, potassium, calcium, magnesium, creatinine, bilirubin, , SGOT, SGPT, LDH, alkaline Phosphatase, γ -GT)
- Assessment of clinical signs or symptoms, toxicity according to NCI-CTC version 4.0
- Endoscopy (incl. biopsy, if patient agrees to participate in translational study)
- Endoscopic ultrasound (optional)
- Tumor Assessment (CT/MRI chest and abdomen)
serum sample (10 ml) for EGFR and ligands determination (if patient agrees to participate in translational study)

